28	Section 6.7.3		Note: The aim for all subjects for the MRA dose should be 50 mg/day. However, the MRA dose must be at least 25 mg/day for at least 1 week for subjects to meet the randomization criteria.	For subjects who are on < 50 mg/day of MRA, double their current dose up to 50 mg/day. Assess tolerance to the 50 mg target dose. MRA dose is at least 50 mg/day and has been stable for at least 1 week

No	Section Number	Descriptive Statement/ Rationale Regarding Revision	Previous Text (If Applicable)	Revised and/or New Text
29	Section 8.2		
 MRA dose is at least 25 mg/day and has been stable for at least 1 week 
If a subject cannot be randomized on the same day the randomization criteria were met, then the subject must be randomized within 1 week and all assessments described in Section 8.2.1 will be performed.
	
If a subject cannot be randomized on the same day the randomization criteria were met, then the subject should be randomized within 1 week and all assessments described in Section 8.2.1 will be repeated on the day of randomization.

30	Section 8.4		
Event Driven EoS Visit Procedures
 
The common end of the study date will be set by the Sponsor based on when the study is projected to accrue the required number of events of CV mortality or CV hospitalization.
 
Investigational sites will be notified of the study termination date approximately 3 months prior to study closure and should advise ongoing study subjects of the study termination date thereafter
	
EoS Visit Procedures
 
The common end of the study date will be set by the Sponsor. The common EoS will occur when 820 subjects have completed the Week 6 visit.
 
Recruitment will be stopped, and subjects called in by the sites for the EoS visit when it is projected that a sufficient number of subjects have been enrolled in order for 820 subjects to reach the Week 6 visit. All randomized subjects, including those who prematurely discontinued patiromer/placebo, will complete the EoS Visit within the timeline provided by the Sponsor around the common EoS date.
 
Investigational sites will be notified of the study termination date as soon as possible after the decision is taken and should advise ongoing study subjects of the study termination date thereafter

31	Section 9.1		-	
The definition of hyperkalemia follows the European Society of Cardiology expert consensus document on the management of hyperkalemia in patients with cardiovascular disease [37]. Hyperkalemia is

No	Section Number	Descriptive Statement/ Rationale Regarding Revision	Previous Text (If Applicable)	Revised and/or New Text
32	Section 10.7.2.1		
Composite Study Endpoints:
 
All events potentially related to the composite primary endpoint of CV death or CV hospitalizations or urgent HF visits will be collected starting from the date of randomization. For the purposes of this protocol, the following events are considered SAEs and must be reported as described in Section 10.7.2.
	
considered for all serum K⁺ values >5.0 mEq/l with the gradings of mild hyperkalemia (serum K⁺ >5.0 mEq ≤5.5 mEq/l), moderate hyperkalemia (serum K⁺ >5.5 mEq ≤6.0 mEq/l) and severe hyperkalemia (serum K⁺ >6.0 mEq).

33	Section 10.7.2.1		
The following CV hospitalization events will be counted towards the primary endpoint:
	
Study Endpoints:
 
All events potentially related to the endpoint of CV death or CV hospitalizations or urgent HF visits will be collected starting from the date of randomization. For the purposes of this protocol, the following events are considered SAEs and must be reported as described in Section 10.7.2.

34	Section 12.2		
Following Claggett (2018), simulations were conducted to investigate the effect of heterogeneity of the subject level exponential risk on the power of the proposed sample size for the primary analysis (log rank test for the time to first occurrence of CV death or CV hospitalization) [39]. Based upon an assumed heterogeneity factor of 4.0 (i.e., gamma frailty with variance of 4.0), the proposed sample will have approximately 80% power. A recurrent event analysis (LWYY test) would have approximately 78% power assuming 30% of events result in death and 20% treatment effect attenuation after each event.
	
The following CV hospitalization events will be counted towards the endpoint:
 
-

No	Section Number	Descriptive Statement/ Rationale Regarding Revision	Previous Text (If Applicable)	Revised and/or New Text
35	Section 12.8.1		
The primary analysis will be based upon the time to the first occurrence of the primary endpoint consisting of a CV death or CV hospitalization (or equivalent in outpatient clinic). The test of significance will be based upon a stratified (randomization strata) log rank test. The treatment effect will be summarized using the HR and 95% CI calculated using a stratified (randomization strata) Cox regression model with treatment as the only model parameter. In these analyses, subjects will be censored as of their last assessment for the primary endpoint as well as for deaths for non-CV causes.
 
Sensitivity analyses for the primary endpoint will be based upon the use of all CV deaths and hospitalizations (i.e., recurrent event analysis) recorded during follow up using the following methods:
 
 — Extended Cox model [2] — Days alive outside of the hospital [3] — Rank based analysis [4] 
Additional descriptive statistics will be calculated to better understand the recurrent events pattern. In particular, the HR will be estimated within event count using a conditional model (gap time method) that allows both the underlying hazard and HR to vary [40] with a robust variance estimator. In this approach, subjects experiencing a death are removed from the risk sets for subsequent events. Additional estimates will be calculated treating CV death as a competing risk for the occurrence of CV hospitalizations
	
The primary analysis will be based upon the mean change in serum potassium levels from Baseline and is analyzed by means of an MMRM approach including all available post baseline data. All analyses will be restricted to serum K⁺ assessments and not substituted by plasma values as they are known to be systematically lower. Central laboratory values and/or local laboratory will be used at all visits, and if both values are present at one visit, then central laboratory values will be used. A Gaussian linear model for repeated measures with treatment, geographic region, sex, baseline T2DM status and visit as factors, and baseline potassium level, baseline eGFR as covariates. The error terms are assumed to follow a multivariate normal distribution with unstructured covariance. Least squares mean changes from Baseline will be reported for both treatment groups with 95% CIs as well as the difference between the least squares group means with 95% CI and p-value testing the null hypothesis of no treatment effect.
 
Sensitivity analyses for the primary endpoint will be based upon the use of all CV deaths and hospitalizations (i.e., recurrent event analysis) recorded during follow-up using the following methods: will explore changes in treatment effect over follow-up time by including treatment by visit interactions in the above-mentioned model.


No	Section Number	Descriptive Statement/ Rationale Regarding Revision	Previous Text (If Applicable)	Revised and/or New Text
36	Section12.8.2		-	
In addition, sensitivity analyses for the primary endpoint will explore changes in treatment effect over follow-up time by including treatment by visit interactions in the above-mentioned model. In addition, sensitivity analyses accounting for potentially informative missingness will be based upon a Win Ratio approach [4,31].
 
Key Secondary Endpoints (Hierarchically Ordered)
 
 • Hyperkalemia events: The time to the first event of hyperkalemia with a serum K⁺ value >5.5 mEq/L as per the measured values from the central or local laboratories is analyzed using a Cox proportional hazards regression model. The event probabilities will be estimated using the Aalen-Johansen estimator of the cumulative incidence function accounting for competing events such as death. • Durable enablement to stay on the MRA target dose (of 50 mg spironolactone or eplerenone): The time to reduction of the MRA dose below target is analyzed using a Cox proportional hazards regression model. The event probabilities will be estimated using Aalen-Johansen estimator of the cumulative incidence function accounting for competing events such as death.

No	Section Number	Descriptive Statement/ Rationale Regarding Revision	Previous Text (If Applicable)	Revised and/or New Text
				
Note: Discontinuation of the target dose for at least 14 days (or less if at the EoS) is required to confirm this endpoint.
 
 Investigator reported AEs of hyperkalemia (first and recurrent) are analyzed using a negative binomial regression with the logarithm of the individual follow-up time as offset. 
A joint frailty model of the total (first and recurrent) hyperkalemia events and time to death as terminating event. If all-cause mortality is substantial in number and differential between the treatment groups, then the joint frailty model would become the main analysis approach.
 
Note: For analyses based upon the negative binomial distribution, the subject level count data will be modeled as function of treatment with the natural log of the subject level follow-up time taken into account in the estimation of the event rate.
 
 Hyperkalemia-related hard outcomes are analyzed using the Win Ratio approach with the following hierarchical components (all assessed during comparable follow-up times) 
 1. Time to CV death 2. Total number of CV hospitalizations 3. Total number of hyperkalemia toxicity events with serum K+ >6.5 mEq/L 4. Total number of hyperkalemia toxicity events with serum K+ >6.0-6.5 mEq/L

No	Section Number	Descriptive Statement/ Rationale Regarding Revision	Previous Text (If Applicable)	Revised and/or New Text
				
5 Total number of hyperkalemia toxicity events with serum K+ >5.0-6.0 mEq/L
 
 • RAASi Use Score which will be analyzed using the Win Ratio approach for each pair of patients at the end of the comparable follow-up period that is appropriate for that pair of patients with the following hierarchical components. Points are accumulated from two components at the respective time for each patient in each comparison: 
Component A:
 
 • If during the follow-up (to the respective end of follow-up in the comparison) there was a death, the subject is assigned 0 points • If during the follow-up (to the respective end of follow-up in the comparison) there was a CV hospitalization, but the subject is alive at the end of that follow-up, the subject assigned 1 point • If during the follow-up (to the respective end of follow-up in the comparison) there was no CV hospitalization and the subject is alive at the end of that follow-up, the subject is assigned 2 points 
Component B:
 
Further points are collected for the treatment status at the respective end of follow-up in the comparison
 
 • For ACEi/ARB/ARNi use: >50% of the target dose = 2 points

No	Section Number	Descriptive Statement/ Rationale Regarding Revision	Previous Text (If Applicable)	Revised and/or New Text
37	Section 12. 8. 3	Secondary	
 Proportion of subjects on $\geq 50\%$ of target dose of ACEi, ARB, or ARNi and $\geq 50\%$ of target dose of MRA at the EoS Visit with analysis using Fisher's Exact Test Total HF hospitalizations (or equivalent in outpatient clinic) analyzed using the negative binomial distribution Change from randomization in the clinical summary score of KCCQ at 8 months 
For analyses based upon the negative binomial distribution, the subject level count data will be modeled as function of
	
 For ACEi/ARB/ARNi use: >0 and up to 50% of the target dose = 1 point For MRA use: $>50\%$ of the target dose = 2 points For MRA use: >0 and up to 50% of the target dose = 1 point For beta-blocker use: $>50\%$ of the target dose = 2 points For beta-blocker use: >0 and up to 50% of the target dose = 1 point 
In summary, each subject in each comparison can have 0-8 points (sum of Components A and B) and all subjects are compared using this score at the respective appropriate follow-up time point.
 
The regression analyses will be adjusted for geographic region as the stratification factor of the randomization and relevant baseline characteristics of the subjects.
 
Other Secondary Endpoints
 
The additional endpoints listed below (Other Secondary Endpoints), will also be summarized descriptively by treatment arm in the full analysis set:
 
 Durable enablement to stay on the target dose of ACE/ARB/ARNi 
Note: Discontinuation of the target dose for at least 14 days (or less if at the EoS) is required to confirm this endpoint

No	Section Number	Descriptive Statement/ Rationale Regarding Revision	Previous Text (If Applicable)	Revised and/or New Text
			
treatment with the natural log of the subject level follow up time taken into account in the estimation of the event rate.
 
The additional endpoints listed below (Other Endpoints), will also be summarized descriptively by treatment arm in the full analysis set:
 
 Emergency treatment for hyperkalemia (hospitalization or emergency room) Patient reported outcome: EQ-5D-5L questionnaire Proportion of subjects with change in the patient reported outcome, KCCQ, greater than 5 points at 8 months after randomization Time to first occurrence of HF hospitalization (or equivalent in outpatient clinic) Total CV hospitalizations (or equivalent in outpatient clinic) Proportion of subjects on any dose of MRA at the EoS Visit Proportion of subjects on any dose of ACEi, ARB, or ARNi at the EoS Visit Change in proteinuria from Screening Change in NT proBNP from Screening Change in high sensitivity troponin from Baseline Functional status by NYHA class 30 day HF re hospitalization after a prior HF hospitalization HEOR analyses 	
 Durable hyperkalemia-free enablement to stay on the MRA target dose (days on 50mg MRA without presence of hyperkalemia) Hyperkalemia toxicity events with serum K+ >6.5 mEq/L Hyperkalemia toxicity events with serum K+ >6.0-6.5 mEq/L Emergency treatment for hyperkalemia (hospitalization or emergency room) Total number of hyperkalemia toxicity events with serum K+ >5.0-6.0 mEq/L KCCQ questionnaire - OSS, CSS and TSS Investigator reported events of hyperkalemia (recurrent events) Proportion of subjects on ≥50% of target dose of ACEi, ARB, or ARNi and ≥50% of target dose of MRA at the EoS Visit Time to first occurrence of CV death or CV hospitalization CV Death

No	Section Number	Descriptive Statement/ Rationale Regarding Revision	Previous Text (If Applicable)	Revised and/or New Text
39	Section 12.9		
Safety Evaluations
 
• Serum K⁺
	
 • First and recurrent CV hospitalizations • First and recurrent HF hospitalizations (or equivalent in outpatient clinic) • Patient-reported outcome: EQ-5D-5L questionnaire • Proportion of subjects on any dose of MRA at the EoS Visit • Proportion of subjects on any dose of ACEi, ARB, or ARNi at the EoS Visit • Change in proteinuria from Screening • Change in NT-proBNP from Screening • Change in high sensitivity troponin from Baseline • Functional status by NYHA class • 30-day HF re-hospitalization after a prior HF hospitalization • HEOR analyses • Changes in serum K⁺ from Baseline to individual visits 
Safety Evaluations
 
 • Laboratory parameters other than those defined as efficacy endpoints
40	Section 12.10		
The blinded monitoring of event rates is planned throughout the study to check the assumptions used for the sample size calculations to predict the timing of interim and final analyses.
 
In addition, an independent DSMB will meet periodically to monitor the study. As part of these reviews, the DSMB will
	No interim analysis is planned.

No	Section Number	Descriptive Statement/ Rationale Regarding Revision	Previous Text (If Applicable)	Revised and/or New Text
41	Section 18		
receive summaries of study conduct measures as well as unblinded safety and efficacy data.
 
To protect the study from prematurely being closed for a finding of efficacy, the DSMB will be requested to use the O'Brien Fleming (Lan DeMets implementation) for evaluating the primary efficacy endpoint in a formal interim analysis of efficacy. A single such evaluation is planned when 50% of the planned primary endpoint events are positively adjudicated.
 
The final analysis will take into account the interim analysis.
 
As such, the significance level at the final analysis will be adjusted, following Lan DeMets, to take into account the exact timing of the interim analysis.
	
 

42	Section 18		-

CI	Confidence interval
CMH	Cochran-Mantel-Haenszel
COVID-19	Coronavirus disease 2019
CRF	Case report form
CV	Cardiovascular
DSMB	Data Safety Monitoring Board
EAC	Event Adjudication Committee
ECG	Electrocardiogram
EF	Ejection fraction
EGFR	Estimated glomerular filtration rate
Eos	End of study
ESRD	End-stage renal disease
ET	Early termination
FAS	Full analysis set
GCP	Good clinical practice
HF	Heart failure
HFrEF	Heart failure with reduced ejection fraction
ICH	International Council for Harmonisation of Technical Requirements for Registration of Pharmaceuticals for Human Use
IVRS	Interactive voice response system
IWRS	Interactive web response system
KCCQ	Kansas City Cardiomyopathy Questionnaire
MedDRA	Medical dictionary for regulatory activities
MRA	Mineralocorticoid receptor antagonist
N	Number
NYHA	New York Heart Association
PD	Protocol deviation
PP	Per protocol
PPS	Per protocol set
PT	Preferred term
PV	Protocol violation
RAASi	Renin angiotensin-aldosterone system inhibitor
SAE	Serious adverse event
SAP	Statistical analysis plan
SD	Standard deviation
SE	Standard error
SOC	System organ class
SOP	Standard operating procedure
SS	Safety set
TEAE	Treatment emergent adverse event
TFL	Tables, figures and listings
TOC	Table of content
WHO	World health organization

1 STUDY DESCRIPTION

Patiromer is being studied in subjects receiving renin angiotensin-aldosterone system inhibitor (RAASi) medications for the treatment of heart failure with reduced ejection fraction (HFrEF). This study will assess the effects of patiromer on serum potassium (K^+) and use of RAASi / mineralocorticoid receptor antagonist (MRA) medications in heart failure (HF) patients.

1.1 Objectives

Study PAT-CR-302 (DIAMOND Study) has the following primary objective:

- To determine whether patiromer treatment of subjects who developed hyperkalemia while receiving RAASi medications will result in changes in serum potassium levels from baseline at randomization

1.2 Study Design

The DIAMOND study is a prospective Phase 3b multinational, multicenter, double-blind, placebo-controlled, randomized withdrawal, parallel group study that includes screening and an up to 12-week Run-in Phase (all subjects will have patiromer initiated and RAASi medications, including MRA, optimized) and a randomized withdrawal Double-Blinded Treatment Phase. The primary efficacy assessment will be based upon the data collected during the Double-Blinded Treatment Phase.

During the Run-in Phase, which is single blind to the subject, the Investigator will manage RAASi initiation and/or dose escalation as recommended by practice guidelines, using clinical judgment to customize RAASi addition or dose escalation based on subject response. Assessment of serum potassium will occur at each visit. The patiromer dose will be titrated based on the subject's potassium level.

After completing the Run-in Phase and found eligible for the Double-Blinded Treatment Phase of the study, subjects will be randomized. Randomized subjects will begin treatment with patiromer or placebo using the same number of packets established for patiromer at the end of the Run-in Phase and will continue the RAASi regimen being administered at the end of the Run-in Phase.

The study will continue until reaching at least the Week 6 visit for each subject. An independent Data Safety and Monitoring Board (DSMB) will act in an advisory capacity to monitor the safety of subjects who participate in this study.

1.3 Method of Assigning Subjects to Treatment Groups

Subjects will be randomized to the treatment arms (1:1 assignment) using permuted block randomization stratified by region. Randomization will take place using a centralized list accessed electronically on the day of randomization after Double-Blinded Treatment Phase eligibility is determined (Day 1).

1.4 Blinding

This is a double-blind study. The sponsor will not have access to unblinded data during the study (with the exception of Viforpha Drug Safety staff in situations where unblinding is necessary to comply with Regulatory requirements), and there is no expectation that the study data (e.g. adverse events, dosing, or lab results) will unblind the sponsor, investigator or subjects. While study data (e.g. serum potassium changes) may provide some suggestion of the assigned treatment, sufficient variability is expected to prevent true unblinding. The DSMB will have access to unblinded study data as needed.

The sponsor, investigator and subjects will not have access to the unblinded DSMB reports, which will be prepared by an independent statistician and programmers not otherwise involved with the conduct of the study.

1.5 Sample Size

The sample size of 410 subjects per treatment arm (total of 820 subjects) has been calculated to provide 90% power to detect a difference between the control group (placebo) and the active group (patiromer) in change in K^+ levels from Baseline. This sample size calculation is based upon the following assumptions: alpha level of 5% (2-sided); difference between group means of 0.116; a SD of 0.5; and 5% loss to follow-up.

2 STATISTICAL METHODOLOGY AND STATISTICAL ANALYSES

2.1 Populations Analysed

Four analysis populations will be defined.

2.1.1 *Randomized Set*

All subjects randomized to study treatment.

2.1.2 *Full Analysis Set*

The full analysis set (FAS) consist of all subjects who satisfy the following criteria:

- Randomized to treatment
- Received at least 1 dose of randomized treatment

The full analysis set will be the primary population used for the evaluation of efficacy.

2.1.3 *Safety Set*

The safety set (SS) consists of all randomized subjects who have taken at least 1 dose of randomized study medication. The subjects in this group will be analysed based on the treatment they received, with data summarized separately for the Run-in and Double-Blinded Treatment Phases of the study.

2.1.4 *Run-in Phase Set*

The Run-in Phase Set will consist of subjects who signed informed consent and received patiromer during the Run-in Phase but were not randomized. This set will be used to summarize safety related events that may be related to patiromer treatment.

At the beginning of the Covid-19 pandemic, in order to ensure subject safety, all subjects who were in the Run-in Phase were discontinued. These subjects were given the opportunity to be re-screened once Covid-19 restrictions were eased in their respective locations. Those who were still eligible were entered into the Run-in Phase again.

Details for handling the adverse event, laboratory and concomitant medication data for subjects with two separate periods of Run-in Phase are provided in the appropriate sections below.

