5.4 Randomization Criteria

Subject may be randomized anytime (but no later than 12 weeks) during the Run-in Phase when they meet all of the following criteria:

1. Current MRA dose is at least the target dose* (e.g., spironolactone 50 mg/day, eplerenone 50 mg/day) and has been stable for at least 1 week.
2. Current ACEi/ARB/ARNi is $\geq 50\%$ of the target dose* and has been stable for at least 1 week.
3. Current patiromer dose is at least 1 packet daily.
4. Current local serum K^+ level is $\geq 4.0 - \leq 5.0$ mEq/L.

* Study-specific target doses as per Table 4 in the Study Manual.

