12.4.3 Safety Set

The safety set (SS) consists of all subjects who have taken at least 1 dose of randomized study medication. The subjects in this group will be analyzed based on the treatment they received with data summarized separately for the Run-in and Blinded Treatment Phases of the study.

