12.4.4 Run-in Phase Set

The Run-in Phase Set will consist of subjects that signed informed consent, entered the Run-in Phase, and received patiromer, but were not randomized. This set will be used to summarize safety related events that may be related to patiromer treatment.

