2.12 Baseline and Screening Definitions

2.12.1 Baseline

Unless otherwise specified, Baseline is defined as the value of a variable at the Day 1/Baseline Visit. If there is a missing value at the Day 1/Baseline Visit, Baseline is defined as the last available non-missing value on or before and ≤ 10 days prior to the first dose of blinded study medication.

For randomized but not treated subjects, Baseline is defined as the value at the Day 1/Baseline Visit; if missing, it is defined as the last available non-missing value on or before and ≤ 10 days prior to the date of randomization

Some laboratory tests are assessed by both the central laboratory and a local laboratory. In these cases, the following baseline values are defined:

- Local Baseline (Bsl_L) is defined as above using only local values
- Central Baseline (Bsl_C) is defined as above using only central values

- Central/Local Baseline (Bsl_CL) is defined as the Central Baseline (Bsl_C) if available, and as the Local Baseline (Bsl_L) if the Central Baseline is missing
- Local/Central Baseline (Bsl_LC) is defined as the Local Baseline (Bsl_L) if available, and as the Central Baseline (Bsl_C) if the Central Baseline is missing

In general, if an analysis includes only local laboratory test results for a specific laboratory test value, Bsl_L is used to calculate change from Baseline and is used as the baseline covariate in models; if the analysis includes only central laboratory test results, Bsl_C is used; if the analysis includes both central and local test results, Bsl_CL or Bsl_LC is used.

Tables and figures will specify what baseline is being used for the table or figure.

The following are specific exceptions to these rules:

- For eGFR, Bsl_CL is defined differently than for other laboratory parameters. The definition is: the value of the Central Baseline (Bsl_C); if missing, the value of the Local Baseline (Bsl_L); if missing, the value at Day 3, with preference for the central value
- Urine ACR is assessed only by the central laboratory, and is collected only during Run-in, at Day 3, Week 2, Week 18, and at each 3-month visit during the Double-blinded Treatment Phase. For analyses of proteinuria, Baseline is defined as the central value of urine ACR at the Day 3 Visit.

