2.17.1 Adverse Events

Adverse events (AEs) and serious adverse events (SAEs) coded using MedDRA (MedDRA version 23.0 or an updated version), including all-cause mortality, will be summarized descriptively.

AE summaries will be provided separately for the Run-in Phase and the Blinded Treatment Phase in the SS.

AE summaries will consist of counts (%) by MedDRA SOC and PT in the Run-in Phase, and by MedDRA SOC, PT and treatment arm in the Treatment Phase. The following types of AEs will be summarized:

- All treatment emergent adverse events (TEAEs)
- TEAEs by severity
- TEAEs related to study medication (patiromer/placebo)
- TEAEs leading to study medication discontinuation (patiromer/placebo)
- SAEs
- SAEs related to study medication (patiromer/placebo)

AE summaries will also be presented in the Run-in Phase Set.

A listing of AEs will be provided, to include verbatim term, preferred term (PT), system organ class (SOC), intensity/severity, relationship to patiromer/placebo, whether serious, onset/end date, action taken and outcome of event.

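### Subjects given patiromer in Run-in, then randomized but never dosed with blinded drug, fall outside both populations used for AE tables, so their Run-in AEs reach listings only

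*SAP*

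**What the plan says.** SAP 2.1.3 defines the Safety Set (SS): "The safety set (SS) consists of all randomized subjects who have taken at least 1 dose of randomized study medication". SAP 2.1.4 defines the Run-in Phase Set as consenting subjects who "received patiromer during the Run-in Phase but were not randomized", and gives its purpose as describing safety events possibly attributable to patiromer.

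The protocol has the same pair of definitions. Section 12.4.3 reads "The safety set (SS) consists of all subjects who have taken at least 1 dose of randomized study medication", and section 12.4.4 takes subjects who entered Run-in and "received patiromer, but were not randomized".

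SAP 2.17.1 places the AE summaries in the SS, separately for Run-in and the blinded phase, and then adds: "AE summaries will also be presented in the Run-in Phase Set". No other population is named for AE tables. The same section brings all-cause mortality under the AE summaries. It also plans a listing of AEs with no population named, and SAP 2.17.3 plans a listing of every death.

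SAP 2.12.1 makes explicit provision for the group at issue: "For randomized but not treated subjects, Baseline is defined as the value at the Day 1/Baseline Visit".

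**The concern.** Anyone who is randomized should already be taking patiromer, because one of the randomization criteria in protocol 5.4 is "Current patiromer dose is at least 1 packet daily". A subject who is randomized but takes no blinded dose therefore carries up to 12 weeks of Run-in exposure to the study drug. The population meant to describe patiromer's safety in Run-in excludes that subject because of the randomization. The SS excludes the same subject because no blinded dose followed.

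Two things are at stake. First, AEs and SAEs that arose on patiromer in Run-in are left out of the tables that readers use to judge its safety. Membership depends on what happened between randomization and first dose. An adverse event or withdrawal at that moment is a plausible reason for not being dosed, although the documents do not say so. Second, Run-in AEs are tabulated in two separate pieces, those later dosed and those never randomized, so no table has all patiromer-exposed Run-in subjects as its denominator.

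**Working it through.** No stated figure underlies this point, so there is none to reproduce. The check is one of set membership, followed by a look at which population each output uses.

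**Step 1: apply the definitions.** The inputs are SAP 2.1.1 to 2.1.4. The rules are:
- Randomized Set = randomized.
- Full Analysis Set (FAS) = randomized and given a blinded dose.
- SS = randomized and given a blinded dose.
- Run-in Phase Set = patiromer in Run-in and not randomized.

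| Patiromer in Run-in | Randomized | Blinded dose | Randomized Set | FAS | SS | Run-in Phase Set | In an AE table |
|---|---|---|---|---|---|---|---|
| yes | yes | yes | yes | yes | yes | no | yes |
| yes | yes | no | yes | no | no | no | **no** |
| yes | no | no | no | no | no | yes | yes |

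The middle row is the only patiromer-exposed combination that belongs to neither AE population. The protocol definitions give the same result.

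**Step 2: look for another output that closes the gap.**
- SAP 2.17.1, AE tables: SS and Run-in Phase Set only.
- SAP 2.17.2, laboratory and vital-sign summaries: SS.
- Protocol 12.9, safety variables: safety set.
- SAP 2.3, disposition: counts randomized subjects and those receiving randomized treatment, and gives early-termination reasons for all randomized subjects. This is not an AE table.
- SAP 2.11: summarizes Run-in hyperkalemia (potassium above 5.5) and hypokalemia events on the Randomized Set, so it includes these subjects for those two outcomes. It is not an AE or mortality table.
- SAP 2.17.1 and 2.17.3: the AE listing and the listing of all deaths would carry these subjects.
- SAP 3, changes from the protocol: does not mention the matter.

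No AE summary table includes the middle row.

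**Step 3: size.** The documents give no count k of undosed subjects. Assume k between 0 and 16 of the planned 820. The share is k/820:
- k = 0: 0%
- k = 1: 1/820 = 0.12%
- k = 4: 4/820 = 0.49%
- k = 8: 8/820 = 0.98%
- k = 16: 16/820 = 1.95%

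Let p be the Run-in AE rate among dosed subjects and q the rate among the undosed. Adding the undosed to the 820 − k dosed shifts the rate by (k/820) × (q − p). With k = 16 and an assumed difference of 10 percentage points, the shift is 0.0195 × 10 = 0.2 percentage points. It would be smaller still against a denominator that also includes the never-randomized.

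**The case against.** A reader might infer that these subjects' events and deaths vanish from the report. The documents do not support that. The AE listing names no population, the death listing covers all deaths with cause and associated AEs, and disposition shows by arm how many were randomized and how many treated. For a handful of subjects, that permits a full case review.

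A reader might also infer that the sponsor expects a sizeable group. The Baseline rule in SAP 2.12.1 shows only that the case was foreseen. Protocol 8.2.1 puts randomization and dispensing of blinded drug at the same Day 1 visit, in subjects already on patiromer, which points to few cases or none.

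Nor is it right that Run-in incidence cannot be derived. The SS and the Run-in Phase Set do not overlap, so their Run-in counts can be added, and SAP 2.3 gives the number who received patiromer in Run-in. Only the undosed subjects' events would have to come from the listing.

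Finally, leaving post-randomization events in undosed subjects out of an SS analysed by treatment received is ordinary practice, not a defect.

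All of this stands, and it limits the consequence. It does not touch the definitional gap: Run-in exposure to patiromer is omitted from the tables intended to describe it, and nothing elsewhere in the SAP or protocol restores it.

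**Conclusion.** The point holds as a gap in the definitions. Subjects with patiromer in Run-in, randomization and no blinded dose are in neither AE population, so their Run-in AEs and SAEs are listed but not tabulated, and no single Run-in AE table covers all exposed subjects. This follows from the definitions and needs no assumption.

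The size does rest on assumption. The number affected is not in the documents, is probably small and may be zero; 0 to 16 of 820 is an illustrative range. Within it the effect on common AE rates is negligible. For a rare SAE, one or two untabulated cases could be a larger share of the total, but the documents give no basis for saying that any exist. The documents do not support a claim that deaths are lost or that the SS is wrongly defined.

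**What to change.** In SAP 2.17.1, base the Run-in AE and SAE summaries on a Run-in safety population: every subject with one or more doses of patiromer in Run-in, whatever happened afterwards. Use four columns: randomized and dosed, randomized but not dosed, not randomized, and total. If nobody was randomized and left undosed, that column shows zero, which is itself informative.

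Keep the existing Run-in Phase Set for its other uses (SAP 2.5, 2.6 and 2.11) and leave the SS unchanged. Report any death or SAE after randomization in an undosed subject in a footnote to the SS tables.

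One further rule needs a decision. SAP 2.17 sends first Run-in data to listings only for subjects who went through Run-in twice, and SAP 2.1.4 explains that the Covid-19 discontinuations created such subjects. The new table would still omit those events unless the SAP says how they are handled, so it should state this explicitly.

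The cost is SAP wording, a combined Run-in AE table in place of two separate ones, and slightly longer tables. No new data are needed.
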